9.4.4 ANALYSIS OF EXPLORATORY ENDPOINTS (BIOMARKERS)

We will compare biological outcomes between treatment arms using the Mann-Whitney U or t-test for numerical endpoints and either χ^2 or Fisher’s exact test for categorical outcomes. Lipid mediators (LM) and specialized pro-resolving mediators (SPM) levels will be analyzed using principal component analysis (PCA).

We hypothesize that treatment with iCO will reduce plasma levels of mitochondrial DNA (mtDNA), IL-18, and receptor-interacting serine/threonine-protein kinase 3 (RIPK3). Circulating IL-18, mtDNA, and RIPK3 levels will be log transformed before analysis. Based on our prior work, the SD of the log-IL-18 is approximately 0.7, approximately 1.0 for mtDNA, and approximately 2.0 for RIPK3. With 12 subjects in the placebo arm and 24 in the iCO arm, we will have 80% power to detect a difference in IL-18 levels of 0.834 log, which corresponds to an approximate 2-fold difference in plasma IL-18. We will have 80% power to detect a difference in mtDNA of 1.190 log, which corresponds to an approximate 3-fold difference in the circulating mtDNA copy number between the iCO and placebo groups.

We will also have 80% power to detect a difference in RIPK3 of 2.38 log, which corresponds to an approximate 8-10-fold difference in the circulating RIPK3 levels between the iCO and placebo groups. While the magnitude of the putative CO effect on these 3 biomarkers is unknown, we found a 3-fold difference in IL-18 between sepsis patients with and without ARDS and a 4-fold difference in mtDNA between sepsis/ARDS patients and controls. Similarly, we found a 7-fold difference in median RIP3K levels between patients with organ failure and shock compared with ICU patients without organ failure or shock. Therefore detecting differences of these magnitudes is feasible in this patient population. Based on our preliminary data, we will also have 80% power ($\alpha=0.05$) to detect a difference in a number of LM and SPM including PGD₂, PGE₂, PGF_{2 α} , TXB₂, RvD2, and Mar1 (**Table 8**).

Table 8. Minimal detectable difference at 80% power.

| | Mediator | Standard Deviation | Detectable Difference (pg/mL) |
|----------------------------|-------------------------------------|---------------------------|--------------------------------------|
| Pro-inflammatory LM | LTB ₄ | 17.95 | 21.4 |
| | PGD ₂ | 0.68 | 0.81 |
| | PGE ₂ | 1.68 | 2.00 |
| | PGF _{2α} | 1.15 | 1.37 |
| | TXB ₂ | 12.38 | 14.75 |
| Pro-resolving SPM | RvD ₂ | 12.18 | 14.5 |
| | Mar1 | 15.29 | 18.2 |
| | RvE1 | 10.54 | 12.55 |

We will assess correlations between biomarkers and clinical and lung physiology outcomes including LIS, SOFA, VFDs, as well as 28 and 60 day hospital mortality. We will use multivariable linear regression as the primary model with LIS as the primary outcome variable. Biomarker levels tend to exhibit right skewedness and large outliers, so data will likely require log transformation. Additional predictor variables (such as demographic variables and comorbidities) will be specified *a priori* and interactions between those variables and biomarkers will be included in the model with adjustment for age and sex as important biological variables. To evaluate the predictive ability of biomarkers for binary outcomes, we will use two methods. We will use c-statistics obtained from a logistic regression model to evaluate the effect of biomarker measurements on increasing the area under the receiver operating characteristic (ROC) curves. In addition, we will test if including measured biomarkers to models including important covariates results in an improvement in the net reclassification index as we have done previously for mtDNA.

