6.3 MEASURES TO MINIMIZE BIAS: RANDOMIZATION AND BLINDING

Eligible participants will be randomized to one of the two treatment arms using a permuted block method¹⁴⁶ with random block sizes. The randomization ratio will be 2:1 iCO:placebo. The randomization will not be stratified by any factors. The study biostatistician will verify all the necessary randomization information (blinding method, randomization method, block size, and number of treatment groups) in the StudyTRAX randomization configuration module.

Site investigators will review all potential study participants with one of the CCC physician members. Following informed consent, the unblinded administering RT or physician or blinded study coordinator will randomize subjects in the database using the StudyTRAX randomization tool. The unblinded administering RT or physician will obtain the subject's treatment assignment through the "View Treatment" button in the blinded database, a privilege granted to unblinded RTs and physicians only. CO-related measurements (SpCO, COHb, ambient CO) and drug-related information will be in a separate project within the database, which the blinded study coordinators will not have access to. Permission to this limited-access project will only be granted to unblinded study personnel by the PI, as it contains treatment-specific information such as CO monitoring and study drug administration data.

The study drug assignment will be blinded to the subject, clinical team, study coordinators, and other study staff with the exception of the administering study staff (RT and physician OR physician alone), who will be unblinded to the treatment assignment to ensure subject safety. We chose this partially double-blind design to ensure safe iCO administration and an unblinded assessment of COHb levels in order not to exceed potentially toxic thresholds.

To maintain blinding, the placebo air cylinders are identical in appearance as the CO cylinders (with the exception of different CGA valves required by the manufacturer Praxair). Cylinders will also be shrouded in dark sleeves to ensure blinding. The placebo air will be administered via inhalation via the COventDS

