8.1.1 STUDY SAMPLE COLLECTION

Sample collection will be done according to the **Schedule of Activities (SoA)** in **Section 1.3**.

COHb Levels: COHb levels will be measured using the IL GEM Premier Co-oximeter at specified time points on Days 1 through 3. See **Section 8.5.3**.

Plasma Samples: Blood (4 mL) will be collected pre-treatment and post-treatment (90 mins and 3 hrs) on days 1-3 in EDTA anti-coagulated tubes for plasma isolation and measurement of biomarkers of mitochondrial dysfunction, inflammasome activation, lipid mediators, and cytokines. Blood (4 mL) will also be collected for plasma isolation on Day 5. Plasma will be obtained and divided immediately after centrifugation into equal aliquots in specified tubes and frozen at -80°C.

RNA Samples: Blood (2.5 mL) will be collected pre-treatment and post-treatment (90 min and 3 hrs) on days 1-3 in Paxgene tubes for RNA isolation, and frozen at -80°C. Blood (2.5 mL) will also be collected in Paxgene tubes for RNA isolation on Day 5 and frozen at -80°C.

DNA Samples: Cell pellets will be obtained for future DNA isolation from the blood collected in EDTA tubes on days 1-3 and on day 5. Cell pellets will be isolated pre-treatment and post-treatment (at 90 min and 3 hrs) on days 1-3.

Primary Cell Isolation: An additional 8 mL of blood will be drawn for isolation of peripheral blood mononuclear cells (PBMCs) pre-treatment on day 1 and post-treatment on day 3. This tube may be used to isolate cell pellets (for future DNA isolation) if unable to obtain an adequate pellet from the 4 mL tube on days 1 and 5.

Urine Sample Collection: Between 50-100 mL of urine will be collected in a sterile specimen container on days 1-3 and on Day 5. Cell pellets will be isolated pre-treatment and post-treatment (at 90 min and 3 hours) to obtain RNA and protein, as well as mtDNA.

Discarded Specimens: Discarded bronchoalveolar lavage (BAL) fluid and plasma will be obtained (when available) for levels of cytokines, mediators/biomarkers, and protein. Plasma and BAL fluid will be divided into equal aliquots in specified tubes and frozen at -80°C.

A total of approximately 90 mL of blood will be collected for research samples during the study from each study subject as follows:

| Sample collection | Day 1 | Day 2 | Day 3 | Day 5 | Total Volume |
|---|----------------|----------------|----------------|----------------|--------------|
| ABG, lactate, and COHb analysis | 3 mL | 3 mL | 3 mL | | 9 mL |

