9.4.3 ANALYSIS OF THE SECONDARY ENDPOINT(S)

We also hypothesize that iCO will reduce the severity of ARDS as measured by lung injury score (LIS), $\text{PaO}_2/\text{FiO}_2$, oxygenation index (OI), and dead space fraction (Vd/Vt). These endpoints will be analyzed using repeated measures analysis of covariance (ANCOVA) to assess the effects of treatment, time, and the interaction between time and treatment, while incorporating between-patient variation in baseline measurements and important covariates including smoking, age, sex, and severity of ARDS. Age and sex will be considered as important biological variables in all analyses.

Interaction contrasts will include polynomial trends across time, focusing on a linear trend suggesting improvement and a quadratic trend suggesting that improvement is leveling off. As part of our analysis, we will also include the interaction between treatment and entry criteria (ARDS/Sepsis vs. Non-ARDS/Sepsis Pneumonia vs. Non-ARDS/non-Sepsis Pneumonia) in the model. Because the study is not powered for the interaction between treatment and entry criteria, that test will be exploratory. We will also perform post-hoc analyses within each criteria group to generate hypotheses for future study.

With 24 subjects in the CO group and 12 subjects in the placebo arm, we will have 80% power ($\alpha=0.05$) to detect a 0.95 difference in LIS between treatment arms, assuming a conservative SD of 0.8 (**Table 7**). We will also have 80% power to detect a 78.6 mm Hg difference in $\text{PaO}_2/\text{FiO}_2$, a 12.0 difference in OI, and a 0.14 difference in Vd/Vt between treatment arms, assuming SDs of 66, 10.1, and 0.12 respectively.

Table 7. Minimal detectable difference at 80% power.

| Endpoint | SD | Detectable Difference ($\alpha= 0.05$) |
|-----------------------------|-----|--|
| LIS | 0.8 | 0.95 |
| $\text{PaO}_2/\text{FiO}_2$ | 66 | 78.6 |

| Endpoint | SD | Detectable Difference ($\alpha= 0.05$) |
|----------|------|---|
| OI | 10.1 | 12.0 |
| Vd/Vt | 0.12 | 0.14 |

Ventilator-free days (VFDs), hospital- and ICU-free days, and Sequential Organ Failure Assessment (SOFA) scores will each be analyzed separately using ANCOVA with treatment arm as the main effect. Given our modest sample size, we will only be powered to see large changes.

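### The biomarker arm comparison in section 9.4.4 uses neither the Day 1 pre-dose level nor the entry-criteria group, which gives up precision in a 24 versus 12 exploratory analysis

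*Combined protocol and SAP*

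**What the plan says.** Section 9.4.4 gives the method for numerical biomarkers: "We will compare biological outcomes between treatment arms using the Mann-Whitney U or t-test for numerical endpoints". IL-18, mtDNA and RIPK3 are log-transformed first, and lipid mediators and SPMs go to principal component analysis. No covariate, change score or time point is named for the arm comparison.

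A baseline exists. Section 8.1.1 states: "Blood (4 mL) will be collected pre-treatment and post-treatment (90 mins and 3 hrs) on days 1-3 in EDTA anti-coagulated tubes", with a further sample on Day 5. That is one Day 1 pre-dose sample and up to nine later ones (two on Day 1, three each on Days 2 and 3, one on Day 5).

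Other endpoints are treated differently. Section 9.4.3 analyses LIS, PaO2/FiO2, OI and Vd/Vt by repeated-measures ANCOVA, "while incorporating between-patient variation in baseline measurements and important covariates", and adds a treatment by entry-criteria term. Sections 9.4.2 and 9.4.5 include entry criteria in the COHb model. Section 6.3 says of the design: "The randomization will not be stratified by any factors".

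Three other statements might seem to fill the gap, but do not:

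- The ANCOVA in 9.4.3 is tied to the four lung endpoints.
- The remark in 9.4.3 that age and sex matter in every analysis covers neither pre-dose level nor entry group, and a two-sample test cannot carry it out.
- The regression at the end of 9.4.4 has LIS as outcome and biomarkers as predictors, so it is not an arm comparison.

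**The concern.** Biomarker levels differ widely between ICU patients. Section 9.4.4 gives these values: "the SD of the log-IL-18 is approximately 0.7, approximately 1.0 for mtDNA, and approximately 2.0 for RIPK3". It also reports that ARDS status matters: "we found a 3-fold difference in IL-18 between sepsis patients with and without ARDS". The expansion to pneumonia without ARDS brings both kinds of patient into one comparison, and randomisation does not balance them by design.

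A two-sample test leaves all of this variation in the error term. If a subject's pre-dose level predicts the later level, adjusting for it removes part of the noise at no cost in samples. The biomarkers carry the mechanism hypothesis in section 9.1, so a true effect could be missed for want of precision that the collected data could supply.

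**Working it through.** **Inputs.** From section 9.4.4: "With 12 subjects in the placebo arm and 24 in the iCO arm", and log SDs of 0.7 (IL-18), 1.0 (mtDNA) and 2.0 (RIPK3). Alpha is 0.05; the section attaches it to the lipid mediators, and it is assumed here to be two-sided and to apply to all three biomarkers. The pre/post correlation (rho) and the share of patients without ARDS are not in the documents; both are assumed and shown as ranges. Natural logs are assumed because they fit the stated fold changes: exp(0.834) = 2.3 and exp(1.190) = 3.3.

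**1. The plan's own figure.** The section states: "we will have 80% power to detect a difference in IL-18 levels of 0.834 log". The ratios to SD are 0.834/0.7 = 1.19, 1.190/1.0 = 1.19 and 2.38/2.0 = 1.19. The standard error of the arm difference is SD × sqrt(1/24 + 1/12) = 0.354 SD. At 1.19 SD the noncentrality is 1.19/0.354 = 3.37, and a t-test on 34 df has 90.5% power (92.0% by normal approximation), not 80%. The 80% detectable difference is 1.02 SD. Taking off the 8% dropout of section 9.2 (22 versus 11) gives 1.07 SD, still short of 1.19. The stated figure is therefore conservative.

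**2. With covariates.** For k covariate degrees of freedom, the residual SD is SD × sqrt(1 − rho²), the error df are 34 − k, and the variance is inflated by 1 + k/(33 − k) for average covariate imbalance. Here k = 1 is the pre-dose level alone. k = 3 adds a three-level entry group with no prognostic value of its own. Power is at a true difference of 1.02 SD, where the unadjusted test has 80%.

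| Assumed rho | Detectable difference, pre-dose only | Detectable difference, plus entry group | Power, pre-dose only | Power, plus entry group |
|---|---|---|---|---|
| 0 | 1.04 SD | 1.07 SD | 79% | 76% |
| 0.3 | 0.99 SD | 1.02 SD | 82% | 80% |
| 0.5 | 0.90 SD | 0.93 SD | 89% | 87% |
| 0.7 | 0.74 SD | 0.77 SD | 97% | 96% |

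Break-even with 1.02 SD is at rho of about 0.18 (pre-dose only) or 0.31 (with entry group). Simulation with 4,000 runs per setting agreed with these powers.

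**3. RIPK3 against its benchmark.** The section's 7-fold benchmark is ln(7)/2.0 = 0.97 SD. Unadjusted, 1.02 SD is exp(2.04) = 7.7-fold, just above it. Adjustment brings 7-fold within reach at rho of about 0.34 (pre-dose only) or 0.42 (with entry group).

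**4. Entry group and IL-18.** A 3-fold gap is ln(3) = 1.10 log. With a share p of patients without ARDS:

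- If 0.7 is the within-group SD, the pooled SD is sqrt(0.49 + p(1 − p) × 1.10²). This is 0.77 at p = 0.1 (up 11%) and 0.89 at p = 0.5 (up 27%). The unadjusted detectable difference is 0.79 to 0.91 log, against 0.74 log with entry group (2 df) in the model.
- If 0.7 is already the total SD, there is no rise. The unadjusted figure is 0.71 log, against 0.65 to 0.46 log adjusted.

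**5. Chance imbalance.** The between-arm difference in pre-dose mean has standard error 0.354 SD. It exceeds 0.3 SD in 40% and 0.5 SD in 16% of randomisations. In the simulated null settings the unadjusted t and Mann-Whitney tests rejected in 5.0% to 5.3% of runs.

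**The case against.** **The section is silent rather than exclusionary.** It names no time point and does not rule out change from pre-dose. This stands: the fault is that the baseline is not written into the plan, not that the plan forbids its use.

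**The gain rests on a correlation that nobody has stated.** This stands. Below about 0.2 to 0.3 adjustment gains nothing, and with two uninformative covariates it costs about 4 points of power.

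**A reader might infer bias,** namely that a chance imbalance in starting level or case mix would produce false CO effects. The documents do not support that. Such imbalance is already in the test's standard error, and type I error stays near 5%. It can pull the estimate in this one trial either way, which is a loss of precision. Nor can imbalance be called as large as a plausible drug effect, because section 9.4.4 says the size of the CO effect is unknown.

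**A reader might also take the 27% rise in IL-18 SD as the expected effect of the expansion.** It is a ceiling. It needs half the patients to be without ARDS and 0.7 to be a within-group SD, and the documents give neither. It also assumes that the gap seen in sepsis patients carries over to this trial's entry groups.

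**The endpoints are exploratory.** This is true, and the safety and COHb accuracy conclusions are untouched.

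**Conclusion.** The point holds as a loss of precision. Section 9.4.4 leaves out a baseline that is already collected and an entry-group factor that three neighbouring sections use, with no stated reason. Relative to 1.02 SD unadjusted, the pre-dose level alone cuts the detectable difference by about 12% at an assumed rho of 0.5 (0.90 SD) and 27% at 0.7 (0.74 SD), and by nothing below about 0.2. The benefit of entry group is supported directly only for IL-18, through the 3-fold gap. The figures assume 24 and 12 evaluable subjects and a two-sided 0.05 test. It does not follow that the study has less power than the protocol claims: the stated 1.19 SD is larger than the unadjusted test needs for 80%.

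**What to change.** In section 9.4.4:

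- Make the main arm comparison for log mtDNA, log IL-18 and log RIPK3 an ANCOVA, or a mixed model for repeated measures, with treatment arm, time, log Day 1 pre-dose level and entry-criteria group. Collapse the group to ARDS versus non-ARDS if the cells are small. Name the treatment contrast in advance.
- Include every randomised and treated subject with any post-dose sample. An analysis resting on a single Day 3 sample would select on status after randomisation, because dosing can be held (section 6.1.6) or end with extubation, death or permanent discontinuation (section 6.1.9).
- Keep the t-test or Mann-Whitney test as a sensitivity analysis.
- For lipid mediators and SPMs, keep the principal component analysis. Apply the same baseline-adjusted model to any single-mediator or component-score comparison, with log transformation where values are skewed (Table 8 is in raw pg/mL).
- Correct the stated 80% power figures, or state the evaluable numbers behind 1.19 SD.

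The cost is SAP wording, one to three degrees of freedom (up to about 4 points of power if neither covariate is prognostic), and a rule for missing pre-dose samples. No new samples or visits are needed. The change should be made before unblinded analysis, so that the covariates are not chosen after seeing results.

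### Section 9.4.4: the RIPK3 detectable difference is wrongly converted and does not follow from its stated inputs, and the 7-fold benchmark lies below it, so feasibility is not shown for RIPK3

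*Combined protocol and SAP*

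**What the plan says.** Section 9.4.4 of the combined protocol and SAP says that IL-18, mtDNA and RIPK3 will be log transformed. It gives SDs on that scale of about 0.7 and 1.0 for the first two and "approximately 2.0 for RIPK3". The group sizes are explicit: "With 12 subjects in the placebo arm and 24 in the iCO arm". The detectable differences at 80% power are 0.834 log for IL-18 (described as about 2-fold), 1.190 log for mtDNA (about 3-fold) and 2.38 log for RIPK3. The plan glosses the RIPK3 figure as follows: "which corresponds to an approximate 8-10-fold difference in the circulating RIPK3 levels between the iCO and placebo groups".

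The section acknowledges that the size of any CO effect on these markers is unknown. It offers earlier between-group contrasts as benchmarks: 3-fold for IL-18, 4-fold for mtDNA and, for RIPK3, "we found a 7-fold difference in median RIP3K levels between patients with organ failure and shock compared with ICU patients without organ failure or shock". It then concludes: "Therefore detecting differences of these magnitudes is feasible in this patient population".

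The planned comparison is given as "We will compare biological outcomes between treatment arms using the Mann-Whitney U or t-test for numerical endpoints". The log base and the sidedness of the test are not stated. An alpha of 0.05 appears in this section only with the lipid mediators.

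**The concern.** The argument is that the trial can detect differences as large as those already seen. That works only if each benchmark is at least as large as the matching detectable difference. It is for IL-18 (3 against about 2) and for mtDNA (4 against about 3). For RIPK3 the order is reversed even in the printed text: the benchmark is 7 and the detectable difference is 8 to 10.

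Two further faults sit under the printed range. The conversion of 2.38 log to a fold-change is off, and 2.38 log is not what the stated SD and group sizes give at 80% power.

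RIPK3 is the only necroptosis marker among the exploratory endpoints in section 9.1, and inhibition of necroptosis is part of the mechanistic hypothesis there. Someone reading a null RIPK3 result against this section could give the trial more credit for sensitivity than it has.

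**Working it through.** **Inputs.** From 9.4.4: RIPK3 SD 2.0 on the log scale; 24 iCO and 12 placebo; 80% power; stated difference 2.38 log; benchmark 7-fold. Assumed: alpha 0.05 two-sided, and a t-test on logs (9.4.4 also allows Mann-Whitney).

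**Step 1: log base.** Compare the printed conversions with each base.

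| Marker | Stated log difference | Printed fold | Base e | Base 2 | Base 10 |
|---|---|---|---|---|---|
| IL-18 | 0.834 | about 2 | 2.30 | 1.78 | 6.82 |
| mtDNA | 1.190 | about 3 | 3.29 | 2.28 | 15.5 |
| RIPK3 | 2.38 | 8-10 | 10.8 | 5.2 | 240 |

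Natural logs are the only base that fits mtDNA, and they also fit IL-18. On that scale exp(2.38) = 10.8. The printed range corresponds to ln 8 = 2.08 and ln 10 = 2.30, so 2.38 lies outside it.

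**Step 2: can 2.38 log be reproduced?** In SD units it is 2.38/2.0 = 1.19. With 24 vs 12, the standard error of the difference in SD units is sqrt(1/24 + 1/12) = 0.3536. The noncentrality is 1.19/0.3536 = 3.37 on 34 degrees of freedom, which gives power 90.5%, not 80%.

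Solving for 80% power at 24 vs 12 gives 1.0196 SD. The detectable difference is then 1.0196 × 2.0 = 2.04 log, and exp(2.04) = 7.7-fold. The normal approximation gives 1.98 log, or 7.25-fold.

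The stated 2.38 is reproduced exactly by 18 vs 9 (1.190 SD, power 80.0%) and nearly by 12 vs 12 (1.197 SD, 2.39 log). The plan states neither set of numbers for this calculation.

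**Step 3: power for the 7-fold benchmark.** ln 7 = 1.946, and 1.946/2.0 = 0.973 SD.

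| Setting | Power for 7-fold |
|---|---|
| 24 vs 12, SD 2.0, two-sided t | 76.2% |
| same, normal approximation | 78.6% |
| same, Mann-Whitney (simulated) | about 74% |
| 24 vs 12, SD 1.9, two-sided t | 80.3% |
| 24 vs 12, SD 2.1, two-sided t | 72.1% |
| 24 vs 12, SD 2.0, one-sided 0.05 t | 85.4% |
| 18 vs 9, SD 2.0, two-sided t | 63.0% |

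**Step 4: the other two markers at 24 vs 12.** IL-18 at 3-fold: ln 3/0.7 = 1.57 SD, power 99%. mtDNA at 4-fold: ln 4/1.0 = 1.39 SD, power 97%. The feasibility statement is sound for both.

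**Step 5: is the 1.19 multiplier peculiar to RIPK3?** No. IL-18: 0.834/0.7 = 1.19. mtDNA: 1.190/1.0 = 1.19. In section 9.4.3, LIS: 0.95/0.8 = 1.19; PaO2/FiO2: 78.6/66 = 1.19; OI: 12.0/10.1 = 1.19; Vd/Vt: 0.14/0.12 = 1.17 after rounding. The same factor runs through both sections, where 24 vs 12 gives 1.02.

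**The case against.** The best defence is that little turns on this. The SD is given only as approximate, and at 1.9 instead of 2.0 the power for 7-fold reaches 80%. Sidedness is not stated, and a one-sided test would give 85%. Feasible is not a promise of 80% power, and about 76% on an exploratory biomarker in a 36-patient Phase Ib trial is not infeasible. The 8-10 range is hedged as approximate, and IL-18 is rounded loosely too (2.30 called about 2). Section 9.2 does not rest the sample size on this calculation. The section also says openly that the CO effect is unknown and that the 7-fold figure contrasts patient groups, so using a non-treatment contrast is disclosed, not hidden.

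Most of that stands, and it limits the size of the point. It does not rescue the text: the printed fold range does not match 2.38 log, 2.38 log does not match the stated inputs, and a benchmark of 7 does not support a conclusion drawn from a threshold of 8 to 10.

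A reader might infer something stronger: that because the stated threshold is really 10.8-fold, the design falls far short for 7-fold. The documents do not support that step. With the stated SD and 24 vs 12, 10.8-fold has 90.5% power, so it is not the 80% threshold and cannot measure the shortfall. The relevant gap is 7.7 against 7. Nor should power be worked out at 22 vs 11 from the 8% dropout in section 9.2. That rate is stated for the COHb precision calculation, and sections 1.4 and 7.2 allow replacement of subjects who are randomized but not treated.

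**Conclusion.** The RIPK3 figures in 9.4.4 are internally inconsistent. The stated 2.38 log is 10.8-fold, not 8-10-fold, and it is not the 80%-power difference for SD 2.0 with 24 vs 12, which is about 2.04 log (7.7-fold). At SD 2.0 the 7-fold benchmark is below the threshold whether one takes the printed range, its correct conversion or the recomputed value. The feasibility conclusion therefore does not follow for RIPK3, although calling it false would go too far: power for 7-fold is about 76%, between 72% and 80% for SDs of 2.1 to 1.9.

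This rests on three assumptions that the plan leaves open: natural logs (well supported by the other two conversions), a two-sided 0.05 test (85% power if one-sided) and all 36 subjects evaluable for RIPK3. If 18 vs 9 was the unstated basis, 2.38 log is right but power for 7-fold is 63%. IL-18 and mtDNA are unaffected. Severity is low, because the endpoint is exploratory and no design decision depends on it.

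**What to change.** In 9.4.4:

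- State the log base and the sidedness of the test.
- Restate the RIPK3 detectable difference as about 2.04 log (7.7-fold) for 24 vs 12. If fewer evaluable subjects were assumed, state the number (18 vs 9 reproduces 2.38 log) and give the fold as 10.8. Changing only the fold to 10.8 while keeping 24 vs 12 would leave a wrong 80% claim.
- Report the power for a 7-fold difference: about 76% at 24 vs 12, or 63% at 18 vs 9.
- Limit the feasibility sentence to IL-18 (99% for 3-fold) and mtDNA (97% for 4-fold), quoted for 24 vs 12, or qualify it for RIPK3.

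Make the change together with a correction or explanation of the 1.19 SD multiplier across 9.4.3 and 9.4.4, so that all the detectable differences rest on the same stated numbers. The cost is a few sentences of text, with no change to design, sample size or data collection. The RIPK3 claim becomes less favourable.
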